6.5 Post-Vaccine Procedures

A. In vitro Immunologic testing

Subjects will have 5mL of peripheral whole blood drawn at multiple time points during the vaccine schedule (pre vaccine, post six vaccines, pre booster 1, pre booster 2, pre booster 3, and completion of all vaccinations) to monitor immunologic responses to the administered vaccines. Subjects will also have the option to undergo additional leukapheresis (10-15 liters) at the completion of the 6 vaccines or completion of the three boosters to obtain T lymphocyte population for additional immunologic analysis. The leukapheresis will be performed in the pheresis facilities at the University of Pennsylvania by certified personnel or at Moffitt Cancer Center, if needed. Attempts will first be made to obtain peripheral access for the pheresis protocol. Subjects will be pheresed 15-20 liters whole blood on a Gambro Spectra or equivalent apparatus. We expect to be able to generate $1-5 \times 10^{10}$ PBMC.

B. Post vaccine laboratory studies

In addition to the blood which will be drawn for the above analyses, an extra tube of serum will be drawn to test the subject's anti-HER-2/neu response. After boost vaccines additional 5 tubes of whole blood will be obtained for immune analysis. These results will be compared with the immune response results that will have been obtained prior to vaccination. An alternative post vaccine leukapheresis can be performed as alternative to blood draws.

- 1. After receiving their vaccines and prior to receiving boost vaccine series, subject will have the following completed:
 - a) CBC w/ differential
 - b) PT/PTT
 - c) electrolytes-Na/K/Cl/CO₂/BUN/Cr/glucose
 - d) liver function tests
 - e) urinalysis
 - f) MUGA or Echocardiogram (Compare to first study)

In addition to the blood drawn for the above analyses, 5 tubes of whole blood will be obtained for immune analysis and tube of serum will be drawn to test subjects anti-HER-2/neu response. These results will be compared with the immune response results that will have been obtained prior to vaccination.

In the event of abnormal symptoms, laboratory monitoring may be done earlier. The laboratory studies and intervals at which they are done will be determined by the PI on a case by case basis.

If significant decline in EF was evident in pre/post vaccine MUGA scan or ECHO, another MUGA scan or ECHO may be performed 1 month post-vaccine, as determined by the PI. Subjects will be closely monitored by the PI, who will determine the need for additional MUGA scan(s) during the 6 month post-vaccine monitoring period on a case by case basis.

C. Long-term Follow-up

After completing the 6 month post-vaccine monitoring period, all subjects will be seen yearly. Mammograms will be obtained at yearly visits if patients have remaining breasts. For Version v2 03/01/2017 30 Pilot Phase I HER-2 Pulsed DC Vaccine to Prevent Recurrence for Patients with HER-2 Driven High Risk Invasive Breast Cancer mastectomy subjects a yearly mammogram of the contralateral breast. This will continue for 5 years.

6.6 Clinical Monitoring

A. Monitor

At University of Pennsylvania, monitoring will be conducted by the PI and the Research Coordinators in accordance with all applicable regulations. Additionally, the PI and RC will meet with the Medical Monitoring Committee as needed to discuss the study and request additional monitoring support as necessary.

At Moffitt Cancer Center, regulatory documents and case report forms will be monitored internally according to Moffitt Cancer Center Monitoring Policies. Monitoring will be performed regularly by the MCC Clinical Monitoring Core for accuracy, completeness, and source verification of data entry, validation of appropriate informed consent process, reporting of SAEs, and adherence to the protocol, Good Clinical Practice (GCP) guidelines, and applicable regulatory requirements.

B. Initial Assessment Monitoring

This serves as early detection and will help identify trouble areas in the study, staff or site early enough in the study to allow corrections which will benefit the study long term. The PI and the RC will meet to review the study data and processes after each treatment (9 total) for the first two subjects. During the initial assessment monitoring, the PI will review all AE/SAE and lab abnormalities with the Radiologist, Medical Oncologist and/or Pathologist (as appropriate). AE/SAEs will be recorded on a study specific Adverse Event form and all SAEs will be reported to the IRB, DSMC, Safety Monitoring Committee, GCRC, FDA, and NIH in accordance with all applicable regulations. All errors will be addressed and corrected at that time and training and study design related issues will be resolved in a timely manner.

C. Ongoing Monitoring

During the course of the trial, safety and data quality monitoring will be performed in an ongoing manner by the PI, RC and other applicable study staff. The RC will monitor the data quality every 6 week (s). This includes ensuring that all source documents exist for the data on the case report forms, ensuring all fields are completed appropriately, all corrections are done according to GCPs and any inconsistencies/deviation are documented. The PI will review the lab results for each patient on an on-going basis and will document his review by signing and dating the lab report. The PI will also review all Adverse Event forms in real-time to ensure appropriateness of the data and timeliness of reporting. All errors will be addressed at the time the monitoring takes place and when the PI reviews the safety data. The PI will also ensure that all renewals are received in a timely manner and all correspondences are documented. Issues related to staff training, protocol design, CRF design and monitoring frequency will be addressed and corrected immediately.

Moffitt Cancer Center

Regulatory documents and case report forms will be monitored internally according to Moffitt Cancer Center Monitoring Policies. Monitoring will be performed regularly by the MCC Clinical Monitoring Core for accuracy, completeness, and source verification of data entry, validation of appropriate informed consent process, reporting of SAEs, and adherence to the protocol, Good Clinical Practice (GCP) guidelines, and applicable regulatory requirements.

D. Data Quality

At University of Pennsylvania the RC will make sure that all CRFs are completed, all changes to CRFs are made in accordance with regulations, source documents exist for all data points, the consent/re-consent process is clearly documented in the source records, investigational agent accountability is maintain proactively and response is clearly documented. Paper CRFs will be utilized until electronic CRFs are available. After the first 1/3 of the subjects are enrolled, the RC and PI will collectively review the charts of 3 randomly selected subjects to ensure compliance with regulations and this plan. The collective review will again occur with a review of 3 subjects drawn from the next 1/3 of accrual and 3 subjects drawn from the final 1/3 of accrual.

E. Safety Monitoring Committee

At University of Pennsylvania in the Department of Gynecology, is in the Department of Medical Oncology will be the Safety Monitoring Committee for this study. Neither is directly involved in the trial. None of these physicians have any clinical trials in association with [name] or for this meeting each committee member will receive a report of all AEs and safety data prepared by the research coordinator. The committee will review all AEs including grading, toxicity assignments, all other safety data and activity data observed in the ongoing clinical trial at this meeting. They may recommend reporting of adverse events and relevant safety data not previously reported and may recommend suspension or termination of the trial. The initial meeting of this committee will be six months after the first patient is enrolled. The final meeting will be six months after the final subject is vaccinated.

F. Study Changes

All changes to the protocol and informed consent will be submitted to the IRB, NIH, FDA and CTSRMC in the form of a formal amendment for approval prior to conducting the study under the proposed changes. If said changes potentially affect the subject's willingness to participate, each subject will be re-consented. Any changes to this monitoring plan will be submitted to the DSMC for approval prior to implementing the changes. In the event of an early study suspension, the PI will immediately notify the IRB, NIH, FDA and CTSRMC.

G. Monitoring Log

At University of Pennsylvania a monitoring log will be completed and maintained to document monitoring by the PI and RC. Moffitt Cancer Center will follow institutional procedures for monitoring of subjects that transfer care to the Center and are newly enrolled at the Center.

H. Auditing

This study will be audited by the Department of Compliance and Monitoring (DOCM) on behalf of the DSMC in accordance with the NCI approved Institutional Data Safety and Monitoring Plan (DSMP).

Moffitt Cancer Center Protocol Monitoring Committee (PMC);

The PMC meets monthly and reviews accrual, patterns and frequencies of all adverse events, protocol violations and when applicable, internal audit results.

Monitoring by the DSMC will be at the following milestones: within 2 weeks of the sixth, or final, vaccination. Two weeks after each boost vaccine and two weeks after completion of post vaccine studies. Monitoring will be conducted on the first three subjects enrolled. The frequency of monitoring of additional subjects (e.g. every other or every third) will be determined after the review of the first three subjects. The frequency of monitoring is subject to change if the DOCM feels it is necessary. The DOCM will be informed when each subject is enrolled, at which time the monitoring visits will be scheduled with the research coordinator.

Moffitt Cancer Center Protocol Monitoring Committee (PMC):

The PMC meets monthly and reviews accrual, patterns and frequencies of all adverse events, protocol violations and when applicable, internal audit results.

6.7 Toxicity and Adverse Event Reporting

A. General Toxicity

The HER-2/neu protein is expressed by the epithelial cells of normal breast, skin, gastrointestinal, respiratory, reproductive and urinary tissues. The HER-2/neu gene is not over-amplified in these normal cells and a level of protein expression is thus expected to be significantly lower than the gene over-amplification and protein over-expression seen in DCIS. In animal models of successful immunity to HER-2/neu protein using HER-2/neu ECD and ICD peptides, no evidence of autoimmunity has been noted. Additionally, in DC trials of melanoma and prostate, no clinical evidence of autoimmunity directed against normal tissues sharing the targeted tumor antigen has been discovered. Therefore, although the risk is presumed to be minimal, the possibility of autoimmune disease directed at these normal tissues cannot be entirely excluded.

This vaccine has not been previously administered to individuals who have been treated with Herceptin. Recent trials of Herceptin, the monoclonal antibody therapy to HER-2/neu ECD, have noted approximately 5% risk of cardiac toxicity leading to heart failure. The mechanism appears to be related to presence of HER-2/neu on cardiac cells. The levels of HER-2/neu expression by cardiac myocytes, however, are extremely low, detectable only by PCR analysis.

Subjects on this trial will have cardiac evaluation of MUGA or echocardiogram to determine their ejection fraction. Subjects will also be closely monitored for signs/symptoms of heart failure. In our first trial there was no evidence of clinically relevant cardiac failure. Less than 8% of subjects had asymptomatic declines in ejection fractions post-vaccine, thought all EFs were still within normal range. There have been no long term cardiac toxicities noted as a result of this vaccine. Additionally, Herceptin does not cause long term cardiac toxicity issues. We do not expect the cardiac toxicity of prior Herceptin treatment and treatment with the vaccine to be additive.

It has been demonstrated that fetuses express HER-2/neu during the third trimester and there is the possibility of spontaneous abortion as a result of anti-HER-2/neu T cell responses against the Version v2 03/01/2017 34

Pilot Phase I HER-2 Pulsed DC Vaccine to Prevent Recurrence for Patients with HER-2 Driven High Risk Invasive Breast Cancer fetus. Therefore women of childbearing years will be made aware of this possibility.

B. Toxicity Definitions

Toxicity will be graded according to the NCI-CTCAE version 4.02

C. Toxicity Definition for Leukapheresis

Grade 1: Requirement for oral calcium supplementation either during or just after procedure. Severe bruising requiring treatment such as warm compresses or anti-inflammatory medication for a brief 1 week duration.

Grade 2: Prolonged requirement for calcium administration greater than 24 hours, infection at the intravenous site requiring treatment or intervention with antibiotics or surgery.

Grade 3: Alteration in vital signs such as severe hypotension requiring hospitalization, hospitalization secondary to infection.

D. Dose Limiting Toxicity (DLT)

Since the agent being administered is a biologic agent prepared from the subjects own cells as opposed to a single drug we will lump the toxicity together as that caused by the process of preparation of the DC vaccine. A subject that develops any grade 3 or greater toxicity per the NIH Cancer Therapy Evaluation Program Common Toxicity Criteria version 4.03 except for fever greater than 40° C for <12 hours will be taken off protocol. A continuous monitoring rule for

dose-limiting toxicity will be followed during the trial, as described in section 6.11 Statistical Considerations.

Grade 2 allergic reaction: generalized urticaria Greater than or equal Grade 3 allergic reaction Greater than or equal Grade 2 autoimmune reaction Greater than or equal Grade 3 cardiac toxicity Any Greater than or equal Grade 3 hematologic and non-hematologic toxicity. Greater than or equal Grade 2 toxicity for leukapheresis

E. Adverse Events

Adverse events will be graded according to NCI Common Toxicity Criteria (version 4.03 seehttps://evs.nci.nih.gov/ftp1/CTCAE/About.html. A copy is enclosed in the Appendix.

1. Adverse Event Reporting

All adverse events will whether or not associated with the study agents be recorded on the CRF. Adverse Events will be reported to the IRB, Data Safety and Monitoring Committee (DSMC), Moffitt Cancer Center Protocol Monitoring Committee (PMC);Safety Monitoring Committee, GCRC, FDA, and NIH. The information collected includes:

•The time of onset of any new adverse event or worsening of a previous adverse event

- •The specific type of adverse reaction in standard medical terminology
- •The duration of the adverse event
- •The grade of the adverse event
- •The attribution of the adverse event to the study reagents

•Description of action taken in treating the adverse event and/or change in study administration of dose

NCI Adverse Event Reporting for Local, Investigator-Initiated Phase I Trials

UNEXPECTI	ED EVENT	EXPECTED EVENT			
Grade 2-3	Grades 4 and 5	Grades 1-3	Grades 4 and 5		
Attribution of	Regardless of		Regardless of		
Possible, Probable	Attribution		Attribution		
or Definite					
Grade 2 – Expedited	Report by phone	Adverse Event	Report by phone		
report to within 10	within 24 hrs.	Expedited Reporting	within 24 hrs.		
working days	Expedited report to	is NOT required.	Expedited report to		
	follow within 10		follow within 10		
	working days		working days.		
Grade 3 – Report by	NOTE: this includes		NOTE: This		
phone/fax within 24	deaths within 30		includes deaths		
hrs. Expedited	days of the last dose		within 30 days of		
reports to follow	of treatment.		the last dose of		
within 10 working			treatment.		
days.					
Creada 1 advisora					
Grade 1 – adverse					
event reporting not					
required					

Adverse events will be reported to the IRB in accordance with their SOPs.

2. Serious Adverse Event Reporting

Deaths that are unforeseen and indicate that other participants or others are at increased risk will be reported to the IRB at the University of Pennsylvania, the Data Safety and Monitoring

Committee (DSMC), Moffitt Cancer Center Protocol Monitoring Committee (PMC); Safety Monitoring Committee, GCRC, FDA, and NIH within 24 hours of the time the investigator becomes aware of the event. Deaths that occur that do not meet the above definition will be reported within 72 hours of the time the investigator becomes aware of the event.

Serious Adverse Events will be reported to the IRB, Data Safety and Monitoring Committee (DSMC), Safety Monitoring Committee, Moffitt Cancer Center Protocol Monitoring Committee (PMC) GCRC, FDA, and NIH.

SAEs will be reported to the IRB promptly within the IRB's guidelines

All on-site SAEs will be sent to Abramson Cancer Center's Data Safety and Monitoring Committee (DSMC) and Moffitt Cancer Center Protocol Monitoring Committee (PMC) according to the following guidelines: all grade 3 or higher events within ten days of knowledge, all unexpected deaths within 24 hours of knowledge, all others deaths within 30 days of knowledge.

All SAE's to the Safety Monitoring Committee and Moffitt Cancer Center Protocol Monitoring Committee (PMC) biannually in a written report including all AE's which will be distributed by intramural mail and email.

All SAE's observed at University of Pennsylvania will be reported to the GCRC promptly, but within three days with a written report of the incident via intramural mail and email.

Serious Adverse Events that are not "unexpected" will be reported to the FDA annually in the Annual Safety Report. SAEs that are drug-related and unexpected will be reported to the FDA within 15 calendar days of discovery of the event via IND safety report. SAEs that are drug-related, unexpected and life-threatening or fatal will be reported to the FDA within 7 calendar days of discovery of the event via IND safety report by telephone or fax. SAEs will be reported to the NIH promptly, but within three days with a written report via email and mail.

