6.9 Statistical Considerations

6.9.1 Design. A single arm phase I trial of HER-2 pulsed DC1 vaccine in subjects with high risk HER-2^{pos} breast cancer with residual disease after neoadjuvant therapy. Subjects will receive 6 weekly DC1 vaccinations and may then be eligible to receive up to 3 boost vaccinations given every 3 months. This study will enroll 18 evaluable subjects. Evaluable implies that a subject received all 6 weekly vaccinations and underwent leukapheresis after the vaccinations for immune response evaluation. Subjects will be followed for 30 days after their *final* vaccination.

6.9.2 Objectives. The primary objectives are to determine feasibility and safety. The secondary objectives are to evaluate immunogenicity and anti-HER2 immunity.

6.9.3 Endpoints. Feasibility is defined as a subject's ability and willingness to complete the treatment regimen (6 weekly vaccinations). Safety is established by grading the observed toxicities using CTC Version 3.0. Cardiac toxicity due to trastuzumab will be monitored 2 weeks after the sixth weekly vaccination (week 8) and at EOS and scored separately from vaccinerelated toxicity. Cardiac toxicity is defined as either asymptomatic change in MUGA (i.e., >20% decline in EF by repeat echo or EF <50%) or symptomatic EF drop or heart failure. Doselimiting toxicity (DLT) due to vaccination is defined as: Grade 2 allergic reaction/generalized urticaria, > Grade 3 allergic reaction/other, > Grade 2 autoimmune reaction, > Grade 2 cardiac toxicity or as specified above, > Grade 3 hematologic and non-hematologic toxicity (except fever) and > Grade 2 toxicity due to leukapheresis. DLT rate will be defined by the weekly vaccination schedule. Toxicities will be scored separately for the maintenance boost schedule. Immunogenicity is evaluated with descriptive statistics and box plots for multiple CD4+ and CD8+ T cell metrics obtained at baseline, 2 weeks after the sixth weekly vaccination (week 8) and after each maintenance boost, as show in the table below. Immune response (IR) is defined as >2 fold increase relative to baseline. Anti-HER2 response will be a quantitated by dilution studies. Long-term anti-HER2 immunity will be assessed at follow-up visits (e.g., q 6 months).

Immune Parameter	Assay Method	Fold change	Response (>2 fold ↑)
Peptide specific reactivities	Tetramer	~	\checkmark
CD8+ T cell activation or tumor recognition	cytokine release	~	\checkmark

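### Fever is treated three ways in the DLT and off-protocol rules, so a severe, prolonged vaccine fever can remove a subject without counting as a DLT

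*Combined protocol and SAP*

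**What the plan says.** Three statements in the combined protocol and SAP bear on fever.

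- **6.7.D, off-protocol sentence.** It applies to "A subject that develops any grade 3 or greater toxicity", "except for fever greater than 40° C for <12 hours will be taken off protocol".
- **6.7.D, DLT list.** It includes any hematologic or non-hematologic toxicity of grade 3 or greater and mentions no fever exception.
- **6.9.3, DLT definition.** It includes "Grade 3 hematologic and non-hematologic toxicity (except fever", where the bracket closes with no limit on temperature or duration.

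For the continuous monitoring rule, 6.7.D sends the reader elsewhere: "as described in section 6.11 Statistical Considerations". In this version Statistical Considerations is section 6.9, and the monitoring boundaries are in 6.9.4.

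The 6.7.D list also contains events below grade 3: "Grade 2 allergic reaction: generalized urticaria", "Greater than or equal Grade 2 autoimmune reaction" and "Greater than or equal Grade 2 toxicity for leukapheresis". In 6.9.3, DLT "due to vaccination is defined as: Grade 2 allergic reaction/generalized urticaria", so grade 2 urticaria is a DLT in both places. The 6.9.3 entries for autoimmune reaction and leukapheresis carry a greater-than sign that may be a greater-or-equal sign lost in the PDF, so nothing below relies on them.

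**The concern.** Section 6.4.6 names fever as the anticipated complication at every vaccine visit, so how fever counts is a practical matter. Two sites reading the same protocol could classify the same fever differently. Under 6.9.3, an event serious enough to end a subject's participation would not enter the DLT count. That count drives the accrual rule in 6.9.4 and the DLT rate reported for the primary safety objective in 6.9.2.

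The secondary matter is that a grade 2 event can be labelled dose-limiting with no dosing consequence written down. During induction the next vaccine is due 8 to 21 days later, and three boosts may follow.

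**Working it through.** **1. The rules side by side.** Placing fever above 40 °C among the grade 3 or greater events follows from 6.7.D, which needs the exception only if such fever would otherwise meet the rule.

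| Vaccine-related event | Off protocol (6.7.D sentence) | DLT (6.7.D list) | DLT (6.9.3) |
|---|---|---|---|
| Fever >40 °C, <12 h | No | Yes | No |
| Fever >40 °C, ≥12 h | Yes | Yes | No |
| Grade 2 generalized urticaria | No | Yes | Yes |
| Grade 2 autoimmune reaction | No | Yes | Sign unclear |

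The second row is the main conflict. The third row is the clearest case of the grade 2 gap.

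**2. The plan's own figures.** For 6.9.4, with the Beta(1,3) prior and x DLTs in n subjects, P(rate > 0.25) = 1 − BetaCDF(0.25; 1+x, 3+n−x). At 2/3, 3/6, 4/9 and 5/12 this gives 0.831, 0.834, 0.842 and 0.852, against the stated 0.83, 0.83, 0.84 and 0.85. For 6.9.6, P(X ≥ 3) with X ~ Binomial(15, p) is 0.764 at p = 0.25 and 0.184 at p = 0.10, against 0.76 and 0.18. All reproduce. The fault lies in which events count, not in the arithmetic.

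**3. What one event does.** One reclassified subject moves the DLT rate by 1/18 = 5.6 percentage points (1/17 = 5.9 with the 17 subjects in 6.9.6). At the six-subject look, 3 DLTs meet the boundary (0.834). If one of the three is an uncounted fever, the posterior is 0.601 and the boundary is not met.

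**4. How often to expect it.** Section 5.3 reports only grade 1 and 2 toxicity in 70 treated patients. Zero in 70 gives a one-sided 95% upper bound of 1 − 0.05^(1/70) = 0.042 for any grade 3 or greater event. With the 80 subjects mentioned elsewhere in 5.3, the bound is 1 − 0.05^(1/80) = 0.037. Section 5.3 adds that the earlier patients had not immediately had chemotherapy or trastuzumab, so the bound may not carry over fully.

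**5. Effect on the accrual rule.** I took looks at 3, 6, 9 and 12 subjects with boundaries 2, 3, 4 and 5, and summed the exact binomial probabilities of first crossing at each look. At a counted rate of 0.10:

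- Look 1: 3(0.10²)(0.90) + 0.10³ = 0.0280.
- Look 2: 0.729 × 0.001 + 0.243 × 0.028 = 0.0075.
- Looks 3 and 4 add 0.0026 and 0.0010, for a total of 0.039.

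In the table, the counted rate under 6.9.3 is the total rate minus the share of subjects whose only DLT is prolonged fever. The totals and the shares are assumptions. The 4.2-point share assigns the whole bound from step 4 to fever, which is an extreme choice.

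| Total DLT rate | Stop, all counted | Stop, 2 points uncounted | Stop, 4.2 points uncounted |
|---|---|---|---|
| 5% | 0.009 | 0.003 | 0.0002 |
| 10% | 0.039 | 0.024 | 0.012 |
| 30% | 0.43 | 0.38 | 0.32 |
| 35% | 0.56 | 0.51 | 0.45 |

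**6. Search for a grade 2 dosing rule.** The post-vaccine assessments in 6.4.6 provide for longer observation, follow-up to resolution and admission if needed. Section 6.9.4 acts on accrual only. Section 6.7.E records any change in dosing after an event but gives no criteria for making one.

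**The case against.** Several points on the other side stand.

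- **Different rules may differ.** The 12-hour limit belongs to the removal sentence, not to either DLT list. A removal rule and an accrual count can have different triggers without conflict. This does not explain why the two DLT lists disagree on fever altogether.
- **That 6.9.3 governs is inferred.** Section 6.7.D refers to Statistical Considerations for the monitoring rule and does not say that its own list gives way. A reader might infer that prolonged fever can never count towards stopping. The documents support that only on one of two readings; under the 6.7.D list it counts.
- **The event would not go unseen.** All graded toxicities are tabulated (6.9.5). The Safety Monitoring Committee reviews all adverse events and may recommend suspension or termination, and the Moffitt committee reviews event patterns monthly (6.6). The 3-of-15 judgement in 6.9.6 refers to unacceptable vaccine-related toxicity and states no fever exemption.
- **The large differences come from strained scenarios.** A reader might take 0.43 against 0.32 as evidence of a seriously weakened stopping rule. That pairing needs a 30% total DLT rate alongside a fever share taken from a bound of 4.2% on all grade 3 or greater events. The remainder would then have to be almost entirely grade 2 DLTs.
- **Little accrual is left to stop.** Sections 2.0 and 6.2 report 15 subjects already enrolled. The target is 18 (17 in 6.9.6), and the boundaries are tabulated only to 12.
- **Grade 2 events are not ignored.** History and examination precede each vaccine (6.4.6), and the PI reviews adverse event forms in real time (6.6). Some of this gap is a rule practised but not written. A reader might infer that a grade 2 DLT should end vaccination permanently. The documents do not require that, and a hold with criteria is enough.

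**Conclusion.** The inconsistency is real: no fever is exempt in the 6.7.D DLT list, all fever is exempt in 6.9.3, and only brief fever above 40 °C is exempt in the off-protocol sentence. On the more natural reading, that 6.9.3 governs, a prolonged severe vaccine fever ends a subject's participation and is left out of both the 6.9.4 rule and the reported DLT rate.

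The expected size is small. At an assumed 10% total rate, the chance of stopping accrual falls from 0.039 to at most 0.012 under the extreme fever share, and most enrolment has already happened. The figures in 6.9.4 and 6.9.6 are correct as stated. Cardiac toxicity has its own boundaries in 6.9.4, which do not depend on the fever exemption. What is mainly at stake is a DLT rate for the primary safety objective that both sites would compute the same way.

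The grade 2 gap is true on the text and secondary. It rests on the absence of any stated action, not on evidence that subjects would be re-dosed carelessly. The textual conflict is certain; the size of its effect depends on the assumed rates.

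**What to change.** 1. Use one DLT list, worded identically in 6.7.D and 6.9.3.
2. In 6.9.3, replace the unlimited fever exemption with an exception for fever above 40 °C lasting under 12 hours. Apply the same exception to the 6.7.D list, so that removal and counting agree on fever.
3. Correct the reference in 6.7.D from 6.11 to 6.9.
4. Add one sentence: after a vaccine-related grade 2 DLT, vaccination is held, with stated criteria for re-dosing or stopping, in both induction and boost phases.

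The cost is wording only, with no extra subjects or procedures. The DLT count under 6.9.3, and so the chance of stopping accrual, may be slightly higher. A few doses may be delayed or missed, and a subject who misses an induction dose would not be evaluable under 6.9.1.
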